6.5 Data Storage

All collected research data will be inputted by the researcher onto REDCap using a pseudo identifier and accessed via an NHS password protected encrypted computer. All physical copies of consent forms, pathway checklists and completed questionnaires will be documented and filed securely in a locked filing cabinet on NHS property within one day of collection. Study pathway visit checklists (Appendix 1) and consent forms will contain

identifiable patient information labels (NHS number, name and date of birth) , these will only be used by the researcher and will not be shared. Data will be given a unique study identifier at the point it is entered onto REDCap.

All participants will be given a unique study identifier which will be recorded on the screening and recruitment log (appendix 1). Patient identifier information will be kept in a separate, password protected database at the point of entry into the DIABETES-PRO study which will document a participants NHS number along with their unique study number.

All data will be stored until data analysis is completed at which point it will be archived in line with Mersey and West Lancashire Teaching Hospitals NHS Trust R&D standard operating procedures (67) . Physical copies of data will be accessed on site (Diabetes Centre, St Helens Hospital) and destroyed when no longer required.

STUDY SETTING

This is a single-centre study. All research activity including participant identification, recruitment, data collection and analysis will be conducted at the Diabetes Centre, St Helens Hospital, [name]. A representative convenience sample will be used of patients who have been referred to the Diabetes centre for support, education and / or advice with their type 2 diabetes or are highlighted via a shared care report as being newly diagnosed with type 2 diabetes in the last month by their primary care provider.

Data will be stored at the Diabetes Centre until the point of data lock (completion of analysis) at which time it will be archived in line with Mersey and West Lancashire Teaching Hospitals NHS Trust R&D guidelines.

SAMPLE AND RECRUITMENT PARTICIPANT ENTRY

8.1 Eligibility Criteria

8.1.1 Inclusion Criteria

All patients with a diagnosis of type 2 diabetes aged ≥ 18 years of age referred to the Diabetes centre who are able to provide informed consent and are responsible for daily management of their diabetes will be screened for entry into the study.

8.1.2 Exclusion Criteria

The following patients will be excluded entry into the study:

- Lack capacity to make an informed decision.
- A diagnosis of type 1, type 3c, Maturity-onset diabetes of the young (MODY) or gestational diabetes.

- Received structured education for their diabetes within the last 12 months either online or face to face.
- Require 1:1 education support e.g., requires interpreter.
- Patients unable to attend for structured classroom education e.g., housebound.

8.2 Recruitment

8.2.1 Sample Size

A sample size of 24-50 participants per group is deemed adequate within a feasibility study to estimate effect sizes and inform future DSME modifications and research (68,69). A sample of 120 patients will be enrolled onto this study allowing for adequate numbers (n=30) across the four groups, controlling for expected participant drop out. Monthly recruitment targets are pre-specified in a study progression criteria table (table 3) to ensure an adequate sample size is achieved for data analysis.

The diabetes outpatient department receives on average 24 referrals for DSME per month with a mean monthly attendance rate of 21 patients. Locally an average of 86 patients are newly diagnosed with type 2 diabetes each month (20), patients who have opted in for data sharing are contacted with an offer of DSME. This has been used to inform realistic recruitment rates. Recruitment rates will be kept under review and discussed with supervisors should the monthly figure fall below projected numbers.

Table 3:Progression criteria and study status

Criterion	Green	Amber	Red
Monthly recruitment	≥ 17 participants	14-16 participants	< 13 participants
Retention rate	>80% at endpoint	60-80% at endpoint	<60% at endpoint

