Background: Structured diabetes self-management education (DSME) is internationally recommended for all people with newly diagnosed type 2 diabetes and is designed to support patients in self-managing their condition and prevent associated long-term complications. DSME is proven to be as effective as pharmacotherapy in preventing diabetes associated morbidity and premature mortality but attendance at both a national and local level remains poor. Local records suggest that of those that start DSME (9%) only 12.6% complete the programme. Attendance at DSME is currently benchmarked as having completed a registration form and had at least one active engagement with a programmes content, with 'completion' measured against ≥60% completion despite landmark trials reporting outcomes based on the full completion of a programme. Little is known, of the effectiveness of DSME on the psychological and emotional health of people with diabetes who complete less than the full DSME programme.

Aim: This feasibility study will test the impact of differing completion rates of a face-to-face DSME programme on patient reported outcomes measuring self-care, diabetes distress and quality of life in people with type 2 diabetes.

Methods: Using a quantitative approach, a single centre, randomised feasibility study will be conducted, aiming to recruit 120 eligible people with type 2 diabetes due to attend a secondary care diabetes clinic in the Northwest UK for specialist support, education and advice. Participants will be randomised into one of four groups: Group 1 will receive a full DSME programme, Group 2 will receive 60%, Group 3 will receive 10% and Group 4 will have delayed education. Normal clinical care will continue. Preliminary outcomes (psychometric questionnaire scores measuring ability to self-care, diabetes distress and health related quality of life) will be evaluated at baseline and 3-4 months post-intervention. Measures of feasibility (eligibility, recruitment and retention rates) will be

reported.

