Intervention • How is the intervention different from normal care? • What does it look like? • Is it clear when it starts and finishes?	Clinical intervention of participants will not be altered. Participants will receive the same DSME programme as routine clinical patients. Normal delivery of DSME programmes is by a diabetes specialist nurse or dietitian. Research DSME programmes will be, where possible, delivered by the researcher for consistency. Participants will be reminded at the beginning of the DSME programme that this is a research study and that some participants will leave after 36 minutes, 3 hours and 36 minutes, with others remaining for the full 6 hours programme. Reminders will be given at the time points in which participants from groups 2 and 3 should leave.
Contextual information • Policy initiatives related to the intervention?	DSME is NICE recommended for all patients newly diagnosed with type 2 diabetes with annual refresher thereafter (15). The National Diabetes Audit suggests 71% of people with type 2 diabetes are offered DSME, with an average attendance rate of 7%. Local records suggest that of those that start DSME (9%) only 12.6% complete the programme (20).

Visit 3

Between 3-4 months post intervention participants will be asked to repeat baseline psychometric tests. For participants in group 4 this will be 4 months from enrolment. This will be the end of the study.

At the end of the study participants in groups 2, 3 and 4 will be offered a full DSME programme.

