3. Patients who have opted into data sharing and have been diagnosed with type 2 diabetes within the last month in primary care are reported via the shared care record, called and offered DSME. As part of this process potentially eligible participants will be screened and identified by the researcher. Potentially eligible participants will be asked as part of the DSME booking process if they would like information on the research. Where potential eligible participants agree a letter (appendix 1, telephone screening letter) will be sent out with a PIS and a screening appointment will be made with the researcher. Screening appointments will be offered either at the Diabetes Centre or as a home visit. Following screening, where eligible participants agree to be involved in the research and provide written informed consent, they will be enrolled in the study.

The researcher is employed as a diabetes clinical research fellow in the Diabetes Centre at St Helens Hospital and therefore already a member of the patients existing clinical team, however, is not providing direct clinical care to any potential participants. Clinical appointment lists and patient records will be obtained by the researcher in her existing NHS role. Sampling will continue until the required number of participants are recruited.

A screening and recruitment log will be stored in the study file and will include the following information: patient initials, screening outcome date of consent, if consent was refused, did/did not meet inclusion/exclusion criteria, date entered the study, unique identifier, randomisation group, study status (ongoing, withdrawn, completed, died) (70,71). A blank copy of the screening and recruitment log is included in appendix 1. Mersey and West Lancashire Teaching Hospital NHS Trust R&D department will be informed of all participants recruited to the DIABETES-PRO study.

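### Table 3 gives no status to a month with exactly 13 recruits: amber covers 14 to 16 and red starts below 13

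*Combined protocol and SAP*

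**What the plan says.** Section 8.2.1 (Sample Size) introduces the table with the words "Monthly recruitment targets are pre-specified in a study progression criteria table". In Table 3 the monthly recruitment row is green at 17 or more, amber at "14-16 participants" and red at "< 13 participants". The retention row below it is green above 80%, amber at "60-80% at endpoint" and red below 60%.

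The same section says that recruitment rates are kept under review and "discussed with supervisors should the monthly figure fall below projected numbers". Section 8.2.2 (printed as 8.2.21.2.2) adds: "Sampling will continue until the required number of participants are recruited". The Abstract names what will be reported on feasibility: "Measures of feasibility (eligibility, recruitment and retention rates".

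**The concern.** Recruits are counted in whole people, so red below 13 means 12 or fewer. Amber begins at 14, which leaves 13 between the two bands. The retention row has no such hole, so this looks like a slip at one boundary and not a deliberate choice.

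What is at stake is pre-specification. A traffic-light table in a feasibility study is useful because each result has its label before anyone has seen it. If a month closes at 13, someone must choose between amber and red with the count already known.

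**Working it through.** **Inputs.** From Table 3: recruitment green at 17 or more, amber 14 to 16, red below 13; retention green above 80%, amber 60% to 80%, red below 60%. From section 8.2.1: planned total 120. The plan gives no expected monthly enrolment and no variance for it, so the means used in step 4 are assumptions.

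**Step 1: recruitment row, single-month counts.** Each whole number from 0 to 120 was tested against the three bands as printed.

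| Monthly count | Band met |
|---|---|
| 0 to 12 | red |
| 13 | none |
| 14 to 16 | amber |
| 17 to 120 | green |

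One count meets no band, and no count meets two.

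**Step 2: retention row, for comparison.** Every rate k/n with n from 1 to 120 falls in exactly one band. At the upper boundary, for example, 96/120 = 80.0% is amber and 97/120 = 80.8% is green. The fault is confined to the recruitment row.

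**Step 3: the same row read as an average.** Table 3 does not say whether the criterion is applied month by month or to a mean rate. For a mean rate, the printed bands leave out values from 13 up to 14, and also values between 16 and 17. For example, 116 recruits in 7 months is 116/7 = 16.6 per month, which is neither amber nor green. Closing the gap at 13 alone would leave this second one open.

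**Step 4: how often 13 might occur.** Assume that monthly counts are Poisson with mean m, so that P(X = 13) = e^(-m) × m^13 / 13!. The months needed to reach 120 are 120/m rounded up, and the expected number of unlabelled months is the product of the two.

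| Assumed mean m | P(X = 13) | Months to 120 | Expected months at 13 |
|---|---|---|---|
| 14 | 0.106 | 9 | 0.95 |
| 16 | 0.081 | 8 | 0.65 |
| 17 | 0.066 | 8 | 0.53 |
| 20 | 0.027 | 6 | 0.16 |

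Rounding up counts a part month as a full one. At a mean of 17, the unrounded 120/17 = 7.06 months gives about 0.46 instead of 0.53. These figures support an order of magnitude only: about one month at most.

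**Step 5: candidate corrections.** Amber 13-16 with red below 13, and amber 14-16 with red below 14 (the same as 13 or fewer), each give every count from 0 to 120 exactly one status. The two differ only in the colour of a month at 13, so the share of months affected is the P(X = 13) column above.

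**The case against.** The strongest reply is that nothing in the plan turns on the label. No action is attached to amber or red. Any month below projected numbers goes to the supervisors whatever its colour. If the projection is the green figure of 17, which is the natural reading although the plan does not define it, a month of 13 already triggers that discussion. Sampling then continues to the target. All of this stands, and it is why the point is minor. It does not give 13 a status.

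It could also be said that a sign was lost when the PDF was read and that red was meant to include 13. That cannot be fully excluded. However, the greater-than-or-equal sign in the green cell of the same row survived, which makes it unlikely, and the sponsor can settle it at once.

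A reader might infer more than the gap supports. One inference is that the progression criteria as a whole are unreliable. Step 2 does not bear that out: the retention row is complete, and as it names no group and refers to the endpoint, its ordinary reading is a whole-study rate of people reaching Visit 3, where "Between 3-4 months post intervention participants will be asked to repeat baseline psychometric tests". Another is that the sample size or the analysis is affected. Neither uses the colour bands.

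**Conclusion.** The gap is real and can be seen in the table itself: a month with exactly 13 recruits has no status. This is a drafting error at the boundary between amber and red, and it is minor. For single-month counts it concerns one integer. If the criterion is meant for an average rate, values between 16 and 17 are uncovered as well. That the gap exists needs no assumption beyond reading the table as printed. The estimate of about one unlabelled month at most rests on the Poisson assumption and on means of 14 to 20 per month, neither of which is in the documents. The documents do not show whether 13 was meant to be amber or red.

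**What to change.** State which band holds 13, and decide it without looking at any month's count. Two forms close the gap:

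- amber 13-16 with red below 13; or
- amber 14-16 with red below 14.

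Say also whether the criterion applies to each month or to an average. If it is an average, write amber as at least 13 (or 14) and below 17, with red below the same lower limit. That wording works for single-month counts too.

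The edit is a few characters in one table row. It still counts as a minor protocol revision: section 10.5 requires agreement with the Chief Investigator and the supervisory team and a new version number, and Appendix 2 requires amendments to be approved by the sponsor before they go to the REC. No sample size, analysis or participant procedure changes.

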8.2.21.2.2 Sample identification and technique

A convenience sample of 120 participants will be recruited for this study through three existing streams with potentially eligible participants added to the screening log sheet (appendix 1) and the pre-visit 1 section of the DIABETES-PRO study visit 1 pathway will be completed (appendix 1).

1. Clinic lists of new patients due to attend the diabetes centre at St Helens Hospital are available on the hospital patient administration system. The hospital electronic record will be used to screen for potentially eligible participants from the clinical list by the researcher. Potentially eligible participants due to attend new patient clinic will be invited into the study by letter (appendix 1, NP clinic screening letter) with attached PIS which will be posted ahead of their clinical appointment. On the day of their clinical appointment the researcher will meet potentially eligible participants to check they received the PIS and to answer any questions. Where potentially eligible participants agree they will be invited for

screening. Following screening, where eligible participants agree to be involved in the research and provide written informed consent, they will be enrolled in the study.

2. Patients who have been referred by their GP for DSME are called and offered education. Education referrals will be used to screen for potentially eligible participants from those awaiting a DSME appointment by the researcher. Potentially eligible participants will be asked as part of the DSME booking process if they would like information on the research. Where potential eligible participants agree a letter (appendix 1, telephone screening letter) will be sent out with a PIS and a screening appointment will be made with the researcher. Screening appointments will be offered either at the Diabetes Centre or as a home visit. Following screening, where eligible participants agree to be involved in the research and provide written informed consent, they will be enrolled in the study.
3. Patients who have opted into data sharing and have been diagnosed with type 2 diabetes within the last month in primary care are reported via the shared care record, called and offered DSME. As part of this process potentially eligible participants will be screened and identified by the researcher. Potentially eligible participants will be asked as part of the DSME booking process if they would like information on the research. Where potential eligible participants agree a letter (appendix 1, telephone screening letter) will be sent out with a PIS and a screening appointment will be made with the researcher. Screening appointments will be offered either at the Diabetes Centre or as a home visit. Following screening, where eligible participants agree to be involved in the research and provide written informed consent, they will be enrolled in the study.

The researcher is employed as a diabetes clinical research fellow in the Diabetes Centre at St Helens Hospital and therefore already a member of the patients existing clinical team, however, is not providing direct clinical care to any potential participants. Clinical appointment lists and patient records will be obtained by the researcher in her existing NHS role. Sampling will continue until the required number of participants are recruited.

A screening and recruitment log will be stored in the study file and will include the following information: patient initials, screening outcome date of consent, if consent was refused, did/did not meet inclusion/exclusion criteria, date entered the study, unique identifier, randomisation group, study status (ongoing, withdrawn, completed, died) (70,71). A blank copy of the screening and recruitment log is included in appendix 1. Mersey and West Lancashire Teaching Hospital NHS Trust R&D department will be informed of all participants recruited to the DIABETES-PRO study.

8.2.3 Informed Consent

The Participant Information Sheet (PIS) and Consent Form is the written information that explains the nature of the research, procedures involved and associated risks. Written informed consent will be obtained before any study specific procedures are undertaken. Informed consent is an ongoing process for all participants. In obtaining and documenting informed consent, the researcher will comply with the applicable regulatory requirement(s) and adhere to Good Clinical Practice and to the ethical principles that have their origin in the Declaration of Helsinki. The European Commission Guidelines state that, 'subjects must be allowed sufficient

time to decide whether or not they wish to participate'. All PIS and consent forms will be identified by the date and version number.

Where possible potentially eligible participants identified through new patient clinic lists will be sent a covering letter (NP clinic screening letter, appendix 1) and PIS ahead of their clinical appointment using an adapted template from the HRA website. On arrival to clinic the researcher will greet the patient and ensure they have read and fully understood the information, answering any questions.

For patients identified through GP education referrals or the shared care record database report for newly diagnosed type 2 diabetes, interested potentially eligible participants will be sent a letter (appendix 1, telephone screening letter) and a PIS ahead of the screening appointment with the researcher. At the appointment with the researcher, either at the Diabetes Centre, or as a home visit, any questions will be answered.

In those agreeing to take part in the research, written informed consent will be obtained and countersigned by the researcher. Two copies will be made: one for the participant and one for scanning onto the patient electronic record by the R&D department with the research records retaining the wet ink version. Consent forms (appendix 1) have been designed using a template from the HRA website.

Recruitment packs will be used which consists of exact copies of the PIS, Consent Form, and an Investigator Consent Process Checklist which will record the participants NHS number, name and date of birth. Recruitment packs will be delivered to the research scanning collection point at the Cancer Research Team Office, St Helens Hospital within 24 hours (or the next working day) for scanning/recording purposes (70,71). Occasionally, consent could be taken but the participant may not meet eligibility after screening procedures, this will be recorded in the study related screening and recruitment log.

ADVERSE EVENTS

9.1 Definitions

Adverse Event (AE): any untoward medical occurrence in a patient or clinical study subject, including unfavourable and unintended signs, including abnormal laboratory results, symptoms or a disease associated with treatment.

Serious Adverse Event (SAE): any untoward and unexpected medical occurrence or effect that:

- **Results in death**
- **Is life-threatening** – refers to an event in which the subject was at risk of death at the time of the event; it does not refer to an event which hypothetically might have caused death if it were more severe
- **Requires hospitalisation, or prolongation of existing inpatients' hospitalisation**
- **Results in persistent or significant disability or incapacity**

- **Is a congenital anomaly or birth defect**

A risk assessment has been carried out for this study. Risks are scored according to severity and likelihood giving an overall risk score (please see figure 5). Identified risks are detailed in table 4.

Peer review feedback highlighted the risk of the researcher knowingly or unknowingly biasing results by supporting participants to complete the PROM tools. This has been risk assessed in table 5. To ensure transparency, support from the researcher will be limited to reading the questions verbatim for each of the PROM tools. This will be done for every participant to standardise the approach.

